Subjects with persistent hyperglycemia (≥ 2 glucose readings ≥ 400 mg/dL, ≥ 3 consecutive glucose readings > 280 mg/dL, or with a mean daily blood glucose concentration ≥ 280 mg/dL) and no treatable intercurrent cause for the hyperglycemia has been identified, will be considered as treatment failure and discontinued from the study. If needed, subjects will be started on continuous insulin infusion.

VII. Study Sites: This study will be performed at Grady Memorial Hospital, Emory University Hospitals, Atlanta, GA, Minneapolis Medical Research Foundation-Hennepin Medical Center, Minneapolis, and The Cleveland Clinic Foundation, Ohio.

VIII. CLINICAL MANAGEMENT GUIDELINES

VIII.a. Admission Laboratory Studies

Standard of care laboratory studies including glucose, HbA1C, and chemistry will be measured on admission and as determined by the treating physician.

For **research purposes** a blood sample will be obtained to measure HbA1C at 1 month and 3 months after discharge. In addition, a urine pregnancy test will be performed, when clinically indicated prior to randomization (in female subjects of child bearing potential only).

VIII.b. Assessment and Monitoring of Hospital Mortality

The investigators and research team will follow study subjects daily and the presumed cause of death will be recorded. Information on the attending physician’s summary of events surrounding subject’s demise will also be documented.

VIII.c. Assessment and Monitoring of Nosocomial Infections

Nosocomial infections will be diagnosed based on standardized CDC criteria (40). New nosocomial infections will not be diagnosed until 48 hours after study initiation to minimize the chance that the infection was actually present (but undiagnosed) prior to study initiation.

The investigators will review each subject’s records regarding potential new infection diagnosis daily on each weekday from Monday to Friday. Data from the weekends will be collected on the following Monday. The coded infection diagnosis and the presumed causative microorganism will be determined daily on a Monday to Friday basis, with weekend data entered on the following Monday.

Aim 1. Inpatient Arm – Flow Chart

Visit Type	Hosp- Day 1	Hosp- Day 2	Hosp- Day 3	Hosp- Day 4	Hosp- Day 5	Hosp- Day 6	Hosp- Day 7	Hosp- Day 8	Hosp- Day 9	Hosp- Day 10
Visit #	1	2	3	4	5	6	7	8	9	10
Time-days	1	2	3	4	5	6	7	8	9	10
Inf. consent	x									
Inclusion/excl criteria	x									
Randomization	x									
Withdrawal criteria	x	x	x	x	x	x	x	x	x	x
Dose adjustment		x	x	x	x	x	x	x	x	x
Efficacy										
Vital signs ¹	x									x
Phys Exam ¹	x									x
Body weight	x									x
BMI	x									x
HbA1c	x									
Fasting BG	x	x	x	x	x	x	x	x	x	x
Pre-meal BG	x	x	x	x	x	x	x	x	x	x
Safety										

Adv events	x	x	x	x	x	x	x	x	x	x
Hypoglycemia	x	x	x	x	x	x	x	x	x	x
Urine pregnancy test	x									x
Trial material										
Drug dispense ²	x									

¹At time of study enrollment and hospital discharge ²As needed

Flow Chart: Aim 2, Outpatient Study

Visit Type	Hospital Day 1	TC	Clinic visit	TC	TC	TC	Clinic visit
Visit #	1	2	3	4	5	6	7
Time-wks	0	2	4	6	8	10	12
Inf. consent	x						
Incl/excl criteria	x						
Randomization	x						
Withdrawal criteria		x	x	x	x	x	x
Drug Compliance		x	x	x	x	x	x
Dose adjustment		x	x	x	x	x	x
Efficacy							
Vital signs	x		x				x
Phys Exam	x		x				x
Body wgt	x		x				x
BMI	x		x				x
HbA1c	x		x				x
Fasting BG	x		x				x
Safety							
Adv events	x	x	x	x	x	x	x
Hypoglycemia	x	x	x	x	x	x	x
Urine pregnancy test	x		x				
CMP or BMP	x		x				x
Trial material							
Drug dispense	x		x				
Drug account	x		x				x

IX. Potential Risks to the Subject:

IX.a. Hypoglycemia. It is possible that following the proposed protocol, patients receiving insulin glargine U300 and U100 may develop hypoglycemia. The risk of hypoglycemia in non-ICU patients treated with subcutaneous insulin is between 5–30% (12, 17, 41, 42). The number of hypoglycemia will be analyzed statistically. For the purpose of this analysis, hypoglycemia is defined as a BG < 70 mg/dL. Severe hypoglycemia is defined as BG < 40 mg/dL.

X. Protection against risks:

We will follow safeguards to minimize the risk to our subjects: a) we will carefully monitor capillary BG at the bedside using a hand-held glucose meter, b) only experienced nurses/or phlebotomist will draw blood samples, and c) women of reproductive age who are sexually active will undergo a urine pregnancy tests prior to participation in the study. To prevent significant clinical events, no patients with history of significant liver, renal impairment or cardiac failure will be recruited in this study.

X.a. Hypoglycemia: We expect that approximately 10% in the inpatient setting and ~20% in the outpatient (post-discharge) arm will experience one or more episodes of hypoglycemia. To minimize the risk of hypoglycemia, the starting dose will be reduced in the basal bolus insulin regimen (TDD: 0.3 units

per kg of body weight) in patients ≥ 70 years of age and/or eGFR < 60 ml/min. To avoid hypoglycemia, the total daily dose of insulin will be decreased by 10% for BG between 70-99 mg/dl and by 20% after each episode of hypoglycemia (BG < 70 mg/dl). In addition, in patients treated with insulin at home, the TDD of insulin will be reduced by 20% on admission and the attending physician may further reduce insulin dose in the presence of severe hypoglycemia.

Hypoglycemia will be treated with dextrose infusion. Dextrose 50% solution will be given for glucose values < 70 mg/dl. If the patient is awake, 25 ml (1/2 amp) will be given IV or oral juice/snack (crackers) as per protocol. If the patient is not awake: 50ml (1 amp) will be given STAT. Blood glucose levels will be repeated in 15 minutes and dextrose administration will be repeated as needed for values < 70 mg/dl.

XI. Inclusion of women.

We anticipate that ~50% of the study subjects will be female. Absence of pregnancy must be demonstrated by blood or urine testing prior to randomization (in female subjects of child bearing potential only). Glargine U300 and U100 have not been approved during pregnancy.

XII. Inclusion of minorities.

Patients will not be excluded based on race or ethnic origin. We anticipate that approximately one-third of patients will be African Americans, Hispanics, and Caucasians.

XIII. Inclusion of children.

No patients under the age of 18 will be recruited in this study.

XIV. Payment for participation.

Participation in this study is voluntary. Patients will receive one hundred dollars (\$100.00) during the hospital stay. If a participant should stop participation before completion, the payment will be prorated at \$10.00 per day. Participants will receive seventy- five dollars (\$75.00) after each clinic visit at 1 and 3 months after discharge. Total compensation will be two hundred and fifty dollars (\$250.00).

XV. Financial conflict of interests.

This study receives support from Sanofi. [name] serves as a consultant to Sanofi and receives compensation for these services. The terms of this arrangement have been reviewed and approved by Emory University in accordance with its conflict of interest policies.

XVI. Pharmacovigilance specifications

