Hypothesis: Treatment with glargine U300 will result in equivalent glycemic control in hospitalized patients with T2D. Glargine U300 will result in lower number of hypoglycemia compared to glargine.

Aim 2: To determine differences in glycemic control after hospital discharge between treatment with glargine U300 and glargine U100 in medicine and surgery patients T2D. Patients with poorly controlled diabetes ($HbA1c \geq 7.5\%$) enrolled in Aim 1 will be invited to participate in this open label prospective outpatient study. The total duration of the study is 3 months. Patients with an $HbA1c$ between 7.5% and 10% will be discharged on preadmission oral antidiabetic agents plus glargine U300 and U100 once daily. Patients with an admission $A1C \geq 10\%$ will be discharged on basal bolus regimen with glargine and glulisine insulin before meals.

Hypothesis: treatment with glargine U300 and U100 will result in a similar improvement in HbA1c levels after hospital discharge. Glargine U300 will result in lower number of hypoglycemia compared to U100.

II. BACKGROUND AND CURRENT STATUS OF WORK IN THE FIELD.

Inpatient glycemic control in non-ICU setting. A large body of evidence has shown that in hospitalized patients, the presence of hyperglycemia and diabetes is associated with increased risk of complications and death (1-6, 28-31). Several randomized multi-center trials have shown that the use of basal bolus insulin regimen result in improved glycemic control and reduced rate of hospital complications compared to sliding scale regular insulin (SSI) in patients with T2D (12-14). We have reported that treatment with basal and basal bolus regimens using glargine U100 results in greater improvement in BG control and a reduction in the frequency of hospital complications including postoperative wound infection, pneumonia, bacteremia, and acute renal and respiratory failure compared to SSI treatment.(16, 17, 32, 33) In addition, the use of basal bolus regimen with glargine U100 is safe with low rate of hypoglycemic events. Based on these studies and others, clinical practice guidelines for the management of hyperglycemia in non-ICU setting have favored the use of basal prandial insulin regimens with insulin analogs for most inpatients with T2D (6, 19, 31).

Efficacy and safety of new glargine U-300 insulin:

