- If a patient develops hypoglycemia (BG <70 mg/dL), the insulin TDD (basal and prandial) should be decreased by 20%.
- If a patient develops severe hypoglycemia (BG <40 mg/dL), the insulin TDD (basal and prandial) should be decreased by 30-40%.

IV.g. Data Analysis:

Aim 1. To determine differences in inpatient glycemic control, as measured by mean daily blood glucose concentration and frequency of hypoglycemia, in general medicine and surgery patients with T2D treated with basal bolus regimen with glargine U300 and U100 plus glulisine insulin before meals.

Due to the lack of efficacy and safety data with the use of glargine U300 in the inpatient setting, periodic conduct interim analyses will be conducted every 6 months to monitor the primary outcome and rate of hypoglycemia, and to modify the study design regarding interval of administration and dosage adjustment for basal insulin (see page 9, Data Safety Monitoring Plan, sections IV. f. and IV.g.).

Sample Size and Power Calculations:

The primary endpoint in this study is glycemic control measured by mean daily BG concentration. To show the non-inferiority of glargine U300 and U100 in terms of glycemic control, we set the equivalence margin as 18 mg/dl (1 mosm/l), from a view that a difference <18 mg/dl is usually not considered as clinically significant (12, 14, 16). Based on the results from Rabbit medicine and surgery trials, it is reasonable to assume the standard deviation of mean daily BG is bounded above by 45 mg/dl. Assuming the true BG difference between the treatment groups is zero, and using one-sided, two-sample t-tests, we require 78 subjects for each treatment group to achieve 80% power. Accounting for 10% attrition rate, we would need 90 patients per treatment group, which means 180 subjects in total, to achieve >80% power in Aim 1.

Analysis of Primary Endpoint:

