V. Aim 2: To determine differences in glycemic control after hospital discharge between treatment with glargine U300 and glargine U100 in medicine and surgery patients T2D.

[figure not shown]
V.a. Rationale. Few studies have addressed the efficacy of insulin alone or in combination with oral agents after hospital discharge. In a recent study (see preliminary results section), patients were discharged on a combination of OADs and glargine U100 insulin or on a basal bolus regimen according to bA1c levels and achieved a marked reduction in HbA1c from 8.75% on admission to 7.9% and 7.35% after 4 and 12 weeks of hospital discharge. However, the use of glargine U100 alone or in combination to oral agents or as basal bolus insulin resulted in 30% and close to 40% incidence of hypoglycemia, respectively. In this study, we will compare the efficacy and safety of glargine U300 and U100 after hospital discharge. The total duration of the study is 3 months. Several outpatient insulin trials have shown that treatment with glargine U300 results in similar improvement in glycemic control, but in significant reduction in hypoglycemia compared to glargine U100 (23-27). Thus we expect that glargine U300 will be a safer alternative to current use of glargine U100 formulation.

V.b Insulin Discharge algorithm:

Patients with poorly controlled diabetes ($HbA1c \geq 7.5\%$) enrolled in Aim 1 will be invited to participate in this open label prospective outpatient study. The total duration of the study is 3 months.

- Patients with admission Hba1c < 7.5% will be discharged on their preadmission antidiabetic regimen and will not be included in the Aim 2 outpatient study.
- Patients with no previous pharmacological treatment prior to admission will be discharged on 50% of daily basal insulin (glargine U300 or glargine U100) hospital dose.
- Patients on oral agents prior to admission with an HbA1c between 7.5% and <10% will be discharged on oral agents plus glargine U300 or glargine U100 at 50% of the daily hospital dose.
- Patients on oral agents prior to admission with an admission A1C ≥ 10% will be discharged on their oral agents plus glargine U300 or glargine U100 at 80% of daily hospital dose. If previous basal bolus only therapy or contraindications to previous oral therapy, discharge on basal bolus at 100% of daily hospital dose.

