GLP1-RA. GLP1-RA treatment is considered background medication (non-investigational medicinal product) and will not be provided during the trial. No dose adjustment or up-titration will occur during the trial.

SGLT2-i. The use of SGLT2-I is considered background medication (non-investigational medicinal product) and will not be provided during the trial. No dose adjustment or up-titration will occur during the trial.

V.c. Hospital Diabetes Education. Prior to discharge, participants will be trained in:

1. Diabetes education if not received within 1 year of admission
2. Recommended targets for fasting and premeal blood glucose between 90 to 130 mg/dL
3. Use of glucose meters for home glucose self-monitoring
4. Keeping BG records, and will receive a logbook to record glucose tests results.
5. Hypoglycemia prevention, recognition and management
6. Insulin administration

V.d. Follow-up Care:

- Provide glargine insulin 1-month supply at each clinic visit.
- A member of the diabetes research team will contact patients via telephone call every 2 weeks for a total of 3 months.
- Patients will be asked to attend outpatient visits at 1 and 3 month after hospital discharge.
- Recommendation on insulin adjustment to be provided after each telephone contact and/or clinic visit by a licensed physician (fellow or study physician) (section V.f).

V.e. During follow up we will collect the following information:

1. Glycemic control:
 - a. Mean daily fasting and premeal blood glucose levels
 - b. HbA1C at 1 and 3 months after hospital discharge
 - c. Hypoglycemic events (BG < 70 mg/dl and < 40 mg/dl)
 - d. Hyperglycemic events (BG > 240 mg/dl)
2. Diabetes treatment:
 - a. Insulin dosage (unit/day)
 - b. Use of oral agents

- c. Protocol adherence
- 3. Clinical Outcome:
 - a. Hospital readmissions
 - b. Emergency room visits
 - c. Postoperative complications

V.f. Primary care physicians will be provided with the following algorithm for outpatient basal insulin dose adjustment every 2 weeks:

Basal Insulin (glargine U300 and glargine U100)	
If mean FBG > 180 mg/dL for the last 3 consecutive days and no hypoglycemia or no random BG (RBG) <70 mg/dL	Increase daily dose by 4 IU
If mean FBG > 140 mg/dL for the last 3 consecutive days and no hypoglycemia < or no RBG <70 mg/dL	Increase daily dose by 2 IU
If mean FBG between 100 - 140 mg/dL and no hypoglycemia or no RBG <70 mg/dL	No Change
If any FBG between 70 – 99 mg/dl	Decrease by 4 IU or 10% of total daily dose

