If any FBG or RBG 40- 69 mg/dl	Decrease by 8 IU or 20% of total daily dose
If any FBG or RBG < 40 mg/dl	Decrease total daily dose by 30 - 40%

V.g. Aim 2. Statistical Analysis:

V.g.1. Sample Size and Power Calculations: The primary endpoint in Aim 2 is difference in glycemic control (mean daily BG) after hospital discharge. Under the same assumptions for equivalence margin and BG variability as in Aim 1, we have the same sample size requirement (i.e. 78 subjects per group after 10% attrition). Accounting for 10% attrition rate, we would need 90 patients per treatment group (total # of patients to be recruited: 180 subjects, 90 per treatment group), to achieve >80% power.

V.g.2. Analysis of Primary Endpoint:

The primary endpoint in this study is glycemic control measured by mean daily BG concentration after hospital discharge. Secondary outcomes include rate of hypoglycemia during follow-up, change in HbA1c, body weight in kilograms, number of episodes of severe hyperglycemia, complications and emergency room visits or hospital readmissions at 12 weeks post-discharge. To analyze these outcomes, we will follow the same analytic strategy proposed for the secondary endpoints of Aim 1. We will first compare the primary outcome using two-sample t-tests (or Wilcoxon tests) or one-way ANOVA, followed by multivariate linear regression to estimate and test the difference between the two treatment groups while simultaneously accounting for other potential confounders. Transformations will be applied if normality violation is detected. Stepwise, backward, or forward model selection strategy will be adopted to determine the variables to be included in the final model. Standard diagnostic and model checking procedures will be applied to examine the fit of the developed models.

DATA HANDLING AND RECORD KEEPING:

Data collection records with personal identifiers will be stored in locked file cabinets. Presentation of the study results at regional or scientific meetings or in publications will not identify subjects. Access to research and confidential records will be limited to clinical investigators, research coordinators, and the IRB at Emory University.

All data will be entered electronically in Redcap by participating sites. Sponsor site expects data to be entered in Redcap within 10 days of phone call or outpatient visit.

VI. Methods and Procedures Applied to Human Subjects:

VI.a. Subject Population:

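### Aim 2 hypothesises similar HbA1c improvement, but its primary endpoint, margin and power concern mean daily glucose, and no rule defines similar for HbA1c

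*Combined protocol and SAP*

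**What the plan says.** Section I.B (Specific Aims) words Aim 2 broadly: "To determine differences in glycemic control after hospital discharge between treatment with glargine U300 and glargine U100". The hypothesis beneath it is specific: "treatment with glargine U300 and U100 will result in a similar improvement in HbA1c levels after hospital discharge". A second sentence of the hypothesis expects less hypoglycemia with U300.

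The statistical section for Aim 2 uses another variable. Section V.g.1 states: "The primary endpoint in Aim 2 is difference in glycemic control (mean daily BG) after hospital discharge". It takes its inputs from Aim 1: "Under the same assumptions for equivalence margin and BG variability as in Aim 1, we have the same sample size requirement". Those inputs, in Section IV.g, are a margin of 18 mg/dl, an SD of at most 45 mg/dl based on two inpatient trials, a true difference of zero, one-sided t-tests, 80% power and 78 per group. Allowing for 10% attrition, 90 per group are to be enrolled.

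Section V.g.2 lists HbA1c among the secondary outcomes: "Secondary outcomes include rate of hypoglycemia during follow-up, change in HbA1c, body weight in kilograms". These follow the analysis strategy for the Aim 1 secondary endpoints: t-tests or Wilcoxon tests, then regression. The primary outcome is likewise compared by t-test, Wilcoxon test or ANOVA, then regression. The margin is not mentioned there.

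On data collection, Section V.e lists "Mean daily fasting and premeal blood glucose levels" and HbA1c at 1 and 3 months. The table headed "Flow Chart: Aim 2, Outpatient Study" has a row for fasting glucose only, at weeks 0, 4 and 12, and a row for HbA1c at the same three times.

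**The concern.** The hypothesis asserts similarity on HbA1c, while everything needed to conclude similarity (a margin, an SD and a power statement) is given for mean daily glucose only. If the report says that the two insulins gave similar HbA1c, the only planned basis is a difference test that failed to reach significance. Such a result may reflect imprecision as easily as similarity.

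Moving the claim to glucose does not fully cure this. The 18 mg/dl margin enters the sample size but not the analysis, so the plan never says what result counts as non-inferior. Nor is the endpoint defined. Section IV.c states for Aim 1 which readings are averaged and over which days; Aim 2 has no counterpart, and Section V.e and the flow chart disagree on which glucose values are collected. Readings, window and analysis could therefore be chosen after the data are seen, in an open-label study.

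**Working it through.** **1. The plan's own figure.** Inputs from Section IV.g: margin 18 mg/dl, SD 45 mg/dl, true difference 0, power 80%. Alpha is not stated; one-sided 0.05 is inferred because it reproduces the figure.

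n per group = 2 × [SD × (z₀.₉₅ + z₀.₈₀) / margin]² = 2 × [45 × (1.645 + 0.842) / 18]² = 77.3, rounded up to 78.

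This matches the stated 78. Power from the noncentral t distribution is 80.0% with 78 per group. With 90 × 0.9 = 81 per group it is 81.3%. The claim of more than 80% is correct for mean daily glucose.

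**2. What carrying it over to HbA1c would require.** The design is sized for a margin of 18 / 45 = 0.40 SD. With 78 per group, 80% power holds for HbA1c only if its margin is 0.40 of the HbA1c SD: 0.40 points at SD 1.0, 0.60 at SD 1.5 and 0.80 at SD 2.0. The protocol's earlier discharge study saw HbA1c fall by 8.75 − 7.35 = 1.40 points at 12 weeks, so these margins are 29%, 43% and 57% of that fall. The documents give no HbA1c margin or SD; all such values here are assumptions.

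**3. HbA1c power with the planned number.** Standard error = SD × √(2/81), which is 0.157, 0.236 and 0.314 points at SD 1.0, 1.5 and 2.0. Non-inferiority power at one-sided 0.05, true difference 0, noncentral t:

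| Assumed SD | Margin 0.3 | Margin 0.4 | Margin 0.5 |
|---|---|---|---|
| 1.0 | 60% | 81% | 94% |
| 1.5 | 35% | 52% | 68% |
| 2.0 | 24% | 35% | 48% |

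Evaluable patients per group for 80% power, by the formula in step 1:

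| Assumed SD | Margin 0.3 | Margin 0.4 | Margin 0.5 |
|---|---|---|---|
| 1.0 | 138 | 78 | 50 |
| 1.5 | 310 | 174 | 112 |
| 2.0 | 550 | 310 | 198 |

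**4. What the planned difference test would show.** Suppose HbA1c truly differs by 0.4 points. The noncentrality, 0.4 / standard error, is 2.55, 1.70 and 1.27 at SD 1.0, 1.5 and 2.0. A two-sided 5% t-test with 81 per group is then non-significant 28%, 61% and 76% of the time.

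**5. The glucose endpoint, place by place.**

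| Item | Aim 1 | Aim 2 |
|---|---|---|
| Readings averaged | Pre-meal and bedtime (IV.c) | Fasting and premeal in V.e; fasting only in the flow chart |
| Window | After the first day of therapy, up to 10 days (IV.c) | Not stated; flow chart shows weeks 0, 4 and 12 |
| Source | Bedside meter (X) | Not stated |
| Margin used in the analysis | – | Not mentioned in V.g.2 |

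**The case against.** The best defence is that Aim 2 itself concerns glycemic control, and Section V.g does supply a sized endpoint with a margin for that. Keeping the Aim 1 endpoint for Aim 2 is a legitimate choice. HbA1c is measured and analysed as a secondary outcome, and the hypoglycemia half of the hypothesis has planned tests. All of this stands. It narrows the defect to the HbA1c sentence of the hypothesis and to the unused margin and undefined glucose endpoint; it does not remove it.

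Three stronger readings are tempting but unsupported.

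- A reader might infer that the stated power is wrong. It is claimed only for mean daily glucose, and it reproduces.
- A reader might infer that HbA1c is certainly underpowered. The documents fix neither margin nor SD: 0.4 points with SD 1.0 gives 81%, and 0.5 with SD 1.0 gives 94%. Baseline adjustment would also help. At SD 1.2 and margin 0.4, unadjusted power is 68%; with an assumed baseline correlation of 0.5 or 0.6 it is 79% or 84%. The power is unstated, not shown to be low.
- A reader might infer that the glucose endpoint comes from patients' home logbooks, with testing that differs by arm. Section V.c provides a logbook as part of diabetes education, but no section names it as the endpoint source, and nothing documents a difference in testing between arms. What can be said is that the source is undefined.

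**Conclusion.** The point holds on the text. The hypothesis names HbA1c; the primary endpoint, margin and power are for mean daily glucose; and no rule says when HbA1c counts as similar. As written, the plan cannot support a conclusion of similar HbA1c. It also lacks an explicit rule and a full definition for the glucose endpoint that it does size.

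The size is necessarily a range: HbA1c power of about 24% to 94%, and a 28% to 76% chance that the planned test misses a 0.4-point gap. Both rest on assumed SDs of 1.0 to 2.0 and on 81 evaluable per arm; the power range also rests on assumed margins of 0.3 to 0.5 points and the inferred one-sided alpha of 0.05. The 81 takes the plan's enrolment at face value. Aim 2 admits only Aim 1 patients with HbA1c of at least 7.5%, so the actual number may be smaller; that is a separate matter. The textual mismatch does not depend on any of these figures. It should be resolved before analysis.

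**What to change.** Reconcile hypothesis and endpoint by one of two routes.

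**(a) Keep mean daily glucose as primary.** Reword the Aim 2 hypothesis to it. State which readings count, from which weeks and from what source, and align Section V.e and the flow chart. State alpha, and in V.g.2 conclude from the confidence interval for the U300 minus U100 difference against 18 mg/dl. Report HbA1c change as a difference adjusted by ANCOVA for admission HbA1c and prior insulin use (the randomization factor in IV.e), with its confidence interval against a pre-stated margin. Say that this comparison is not powered, and do not infer similarity from a non-significant test.

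**(b) Make 12-week HbA1c change primary.** Give a justified margin, SD and alpha, analyse by the same ANCOVA, and restate the power for the planned number. Mean daily glucose becomes secondary.

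Route (a) costs wording and an endpoint definition, plus the admission that HbA1c is unpowered. Route (b) costs a power statement that may be less favourable. If 80% power were to be kept, it could need many more patients: for example 174 or 310 evaluable per group at SD 1.5 with margins of 0.4 or 0.3, before any gain from baseline adjustment. Neither route needs a new HbA1c measurement, because it is already scheduled at baseline, 1 month and 3 months.
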